4.6.7 Follow-Up Assessments

Participants who complete the double-blind treatment period and who are not willing to enroll in an OLE or these who complete the OLE period (defined as administration of at least three 510-mg doses Q4W) and are not willing to enroll in the WN42171 open-label study will be asked to return to the clinic 14 weeks and 50 weeks after the last dose of study drug for the follow-up visits (Follow Up 1 and Follow Up 2 or OLE Follow Up 1 and OLE Follow Up 2, respectively)..

When participants complete the treatment period or discontinue early, every effort should be made to ensure that the safety follow-up period and all related assessments are completed.

After the study completion or early termination visit, adverse events should be followed as outlined in Sections [5.5](#) and [5.7](#). Refer to the schedule of activities (see [Appendix 1](#)) for the list of assessments to be performed at the follow-up visits.

4.6.8 Unscheduled Assessments

Assessments at unscheduled visits should be determined by the investigator based on clinical relevance and appropriateness to the cause of the unscheduled visit. The schedule of activities in [Appendix 1](#) allows for all assessments to be performed at unscheduled visits.

4.7 TREATMENT, PARTICIPANT, STUDY, AND SITE DISCONTINUATION

4.7.1 Study Treatment Discontinuation

Participants must discontinue study treatment if they experience any of the following:

- Any medical condition that the investigator or Sponsor determines may jeopardize the participant's safety if he or she continues to receive study treatment
- Investigator or Sponsor determines it is in the best interest of the participant
- Pregnancy
- Upon evidence of more than 15 ARIA-H, cumulatively
- Any disseminated leptomeningeal hemosiderosis

All participants who withdraw from treatment will be asked to return 2 weeks after last dose in order to complete the early termination visit assessments.

In addition, participants who withdraw from treatment will be asked to return for collection of safety (except MRI) and limited efficacy data (i.e., the primary and secondary endpoints) at visits that have efficacy assessments according to the schedule of activities until the end of the double-blind treatment period, *and then the follow-up visits*, or until the last OLE follow-up visit (OLE Follow Up 2) for those who enrolled in the OLE.

The primary reason for study treatment discontinuation should be documented on the appropriate eCRF. Participants who discontinue study treatment prematurely will not be replaced.

4.7.2 Participant Discontinuation

Participants have the right to voluntarily withdraw from the study at any time for any reason. In addition, the investigator has the right to withdraw a participant from the study at any time. Reasons for withdrawal from the study may include, but are not limited to, the following:

- Participant withdrawal of consent at any time
- Study termination or site closure
- Any medical condition that the investigator *and* Sponsor determines may jeopardize the participant's safety if he or she continues in the study
- Investigator or Sponsor determines it is in the best interest of the participant

- Participant non-compliance with the study and/or study procedures, defined as missing more than three consecutive dose administrations (with Q4W dosing regimen) or more than six consecutive dose administrations (with Q2W dosing regimen) because of non-safety-related reasons or more than half of the dosing visits in a calendar year

All participants who discontinue from the study early will be asked to return 2 weeks after last dose in order to complete the early termination visit.

Participant should be informed of circumstances under which their participation may be terminated by the investigator without the participant's consent. Any administrative or other reasons for withdrawal must be explained to the participant.

Every effort should be made to obtain information on participants who withdraw from the study. The primary reason for withdrawal from the study should be documented on the appropriate eCRF. However, participants will not be followed for any reason after consent has been withdrawn.

Participants who withdraw from the study will not be replaced.

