All participants who prematurely discontinue treatment will continue participating in the study and will be asked to return for collection of safety and limited efficacy data (see Section 4.7.1).

[figure not shown]
Participants will undergo brain MRI examinations for safety monitoring and longitudinal changes in brain structure. MRI scans will be read by a central MRI reader (for more details regarding imaging-related criteria, see Section 4.1.2.2). Participants will also undergo standard tests to monitor safety (blood tests, ECG), as well as the Columbia–Suicide Severity Rating Scale (C-SSRS) to monitor for suicidality, tests for cognition, function, and QoL status. Blood samples for the assessment of PK samples, PD biomarkers, and ADA will be obtained from all participants.

The incidence and nature of adverse events, serious adverse events, ARIA-E, ARIA-H, ISRs, adverse events of special interest, ECGs, and laboratory abnormalities will be assessed on a regular basis by an unblinded iDMC.

An overview of the study design is provided in Figure 7. The schedule of activities is provided in Appendix 1.

Once the double-blind treatment period is completed, participants who consent and are eligible may opt to participate in an OLE. If the stand-alone open-label study (Study WN42171) is not open for enrollment at the time that a participant completes the double-blind treatment period of this study, then the participant will follow the OLE procedures described in this study (Section 4.3.2.2 and Appendix 1). These participants will then transition to Study WN42171 after they have completed the entire schedule of activities in the OLE of this study and the protocol for Study WN42171 is available and approved as per local requirements. If Study WN42171 is open for enrollment at the time that a participant completes the double-blind treatment period of this study, then the participant will enroll directly in Study WN42171 and not in the OLE portion of this protocol. *The OLE of Study WN29922 is not applicable in countries that cannot run Study WN42171.*

Figure 7 Overall Study Design

W=week

The study consists of three distinct periods:

- Screening (including an optional pre-screening): The screening period may last up to 12 weeks for each eligible participant.

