- Double-blind treatment period: After screening, participants who meet all eligibility criteria will be randomly assigned to one of two arms (gantenerumab or placebo) in a 1:1 ratio. Following baseline assessments, each participant will receive a minimum of nine SC Q4W administrations of study drug (uptitration period), followed by up to 40 administrations of study drug in the double-blind treatment period in scenario 1 or up to 46 administrations in scenario 2, if applicable. The last dose of study drug will be administered at Week 114 in scenario 1 and at Week 126 in scenario 2, if applicable. At the end of the double-blind treatment period, 2 weeks after the last dose, all participants will undergo the final safety and efficacy study visit. Participants who have already completed the double-blind treatment period prior to implementation of *the study extension by 12 weeks* will have received 34 SC Q2W administrations of study drug during the double-blind treatment period. The last dose will be administered at Week 102, and their final efficacy and safety visit will be at Week 104.
- Post-double-blind treatment period: After the final efficacy and safety study visit, all participants will be asked to come back for the long-term follow-up visits or to continue in the OLE.

Long-term follow-up: Long-term follow-up will consist of a 50-week follow-up period with evaluations at Weeks 14 and 50 after completion of study drug

administration. Participants who withdraw early during the double-blind treatment period or during the OLE period are also asked to complete the long-term follow-up visits.

OLE: All eligible participants will have the opportunity to enter an OLE study.

- Eligible participants who enrolled early in the WN29922 study may start the OLE as detailed in [Appendix 1](#), [Table 5](#), and [Table 6](#), and will then transition to the open-label Study WN42171 (details will be provided in Protocol WN42171). Participants who terminated the WN29922 OLE early will be asked to come back for long-term follow-up visits.
- If the WN42171 protocol is available and approved by local authorities, the eligible participants will directly be enrolled in the open-label Study WN42171.

For the schedule of activities at each visit, see [Appendix 1](#).

China Enrollment Plan

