4.6.6 Assessments at Study Completion or Early Termination Visit

Participants who complete the double-blind treatment period at Week 114 in scenario 1 or at Week 126 in scenario 2 (if applicable) will have to complete the final efficacy and safety assessment period 2 weeks following the last dose. Some participants may have already received the last study drug administration at Week 102 and performed the final efficacy and safety visit at Week 104 at the time of implementation of *the study extension by 12 weeks*.

All participants will be asked to come back for the follow-up assessments 14 weeks and 50 weeks after the last dose, unless they are transitioning to an OLE.

All participants who withdraw from treatment or discontinue from the study early (during the double-blind treatment period or during the OLE) will be asked to return 2 weeks after the last dose of study drug in order to complete the early termination visit.

In addition, participants who withdraw from treatment will be asked to return for collection of safety (except MRI) and limited efficacy data (i.e., the primary and secondary endpoints) at visits that have efficacy assessments per the schedule of activities until the end of the double-blind treatment period or until the last OLE follow-up visit (OLE Follow up 2) for those who enrolled in the OLE period.

Autopsy reports, including cause of death, for all participants who die during the study (i.e., prior to the Week 50 follow-up visit) should be requested.

Refer to the schedule of activities to be performed at the study completion in [Appendix 1](#).

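### Protocol 4.7.2 permits withdrawal from the study for missed doses alone, and the visits then requested often put no CDR-SB in the Week 116 window, although participants who stop drug are asked to attend Week 116

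*Protocol*

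**What the plan says.** Protocol section 4.7.2 (Participant Discontinuation) provides that "the investigator has the right to withdraw a participant from the study at any time". Among the reasons that may apply it lists non-compliance, defined entirely by missed doses: more than three in a row on four-weekly dosing or, on two-weekly dosing, "more than six consecutive dose administrations (with Q2W dosing regimen) because of non-safety-related reasons or more than half of the dosing visits" (the latter per calendar year). Participants who "discontinue from the study early will be asked to return 2 weeks after last dose" do so for an early termination visit. The section adds: "Every effort should be made to obtain information on participants who withdraw from the study". Follow-up ends once consent is withdrawn.

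For participants who stop drug, section 3.1.1 says: "All participants who prematurely discontinue treatment will continue participating in the study". Section 4.7.1 says that "participants who withdraw from treatment will be asked to return for collection of safety (except MRI) and limited efficacy data" at the scheduled efficacy visits until the double-blind period ends, and section 6.4.1 repeats the request. Section 4.6.6 gives the termination visit to both groups ("All participants who withdraw from treatment or discontinue from the study early") but asks only those who withdraw from treatment to continue with efficacy visits.

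Section 3.1.1 also states: "Participants who withdraw early during the double-blind treatment period or during the OLE period are also asked to complete the long-term follow-up visits". Those visits fall 14 and 50 weeks after the last dose. Appendix 1, Table 3 prints a CDR at the termination visit and at the 50-week visit (Week 164), but none at the 14-week visit (Week 128).

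SAP section 1.2 has the Sponsor stress collection of the primary endpoint through Week 116, but only for people who leave treatment and remain in the study. SAP Table 4 accepts a Week 116 value on study days 771 to 897, or up to the first open-label dose if that is earlier.

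**The concern.** Two routes lead away from dosing, and they carry different follow-up. Section 4.7.1 does not list missed doses among its reasons for stopping drug; section 4.7.2 lists them as a reason for leaving the study. A site looking up what to do about repeated missed doses therefore finds the route with less endpoint follow-up. A participant taken off drug is asked back for Week 116, while one who has simply missed doses may not be.

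What is at stake is avoidable imputation. Under SAP section 5.3.3, values observed after an SDCR intercurrent event are used, and missing ones are imputed from placebo increments (copy increments from reference, CIR). Where such a participant would still have attended, a CDR-SB that could have been collected is replaced by an imputed one. The supplementary treatment-policy and MMRM analyses (SAP 5.3.5.2) also use all observed data and lose the same value.

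**Working it through.** **The plan's own figures.** Four-weekly doses at Weeks 0, 4, ..., 32 number 32/4 + 1 = 9. Two-weekly doses at Weeks 36, 38, ..., 114 number (114 − 36)/2 + 1 = 40. The total is 49, as in Protocol 4.3.2.1. With day = 7 × week + 1, Week 116 is Day 813, the target day in SAP Table 4. The window of Days 771 to 897 is then Weeks 110 to 128.

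**Last-dose weeks L from which a consecutive-miss criterion can be met by Week 114.**
- Four-weekly: the fourth miss falls at L + 16. All 9 weeks qualify.
- Two-weekly: the seventh miss falls at L + 14, so L ≤ 100. Weeks 36 to 100 give (100 − 36)/2 + 1 = 33.
- Total 9 + 33 = 42.

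**When a CDR falls in Weeks 110 to 128.**
- The 50-week visit needs 110 ≤ L + 50 ≤ 128, so L = 60 to 78, which is 10 weeks.
- The termination visit on its printed date needs L + 2 ≥ 110, so L ≥ 108. None of the 42 qualifies.
- That printed date has already passed by 12 weeks (two-weekly) or 14 weeks (four-weekly) when the criterion is met. If the visit is held at that point instead, L + 14 ≥ 110 gives L = 96, 98 and 100, which is 3 weeks.
- The 14-week visit has no CDR printed.

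| Last-dose week | Count | Printed dates | Termination visit when criterion met |
|---|---|---|---|
| 0–32 | 9 | none in window | none in window |
| 36–58 | 12 | none in window | none in window |
| 60–78 | 10 | 50-week visit | 50-week visit |
| 80–94 | 8 | none in window | none in window |
| 96–100 | 3 | none in window | termination visit |

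Without a requested CDR-SB in the window: 9 + 12 + 8 + 3 = 32 of 42 on printed dates, or 9 + 12 + 8 = 29 of 42 with the later termination visit. Under 4.7.1 a Week 116 visit is requested for all 42.

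**Sensitivity.** Protocol 4.6.3 allows assessments up to 4 weeks out of window in exceptional circumstances. Applied to the 50-week visit, this widens L to 56 to 82 (14 weeks) and gives 28, or 25 with the later termination visit.

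**Which analyses use the value.** After an SDCR event, observed values enter the primary analysis. After an event that is not study drug or condition related (NSDCR), they are removed (SAP 5.3.3), so nothing is lost there. COVID-19 withdrawals and purely administrative ones are NSDCR (SAP Table 3).

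**Sample-size allowance.** A difference of 0.3 × 2.5 = 0.75, SD 2.97, two-sided 5% and 90% power give 330 per arm, 660 in total. Then 660/0.65 = 1,015.4, rounded up to 1,016, as stated in Protocol 6.1. Losses within that allowance of about 35% leave planned power unchanged.

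**The case against.** The strongest reply is that nothing forces the loss. Section 4.7.2 gives reasons that may apply, and an investigator can keep the participant on the 4.7.1 route. A reader might infer that the two sections contradict each other, or that missed doses must end participation. The text supports neither: the clause is permissive, and the retention sentences concern people who stop drug.

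Other routes to a value also exist. Section 4.6.8 and Appendix 1 allow any assessment, including the CDR, at an unscheduled visit, and SAP 5.3.3 accepts unscheduled assessments in its windows. Section 4.7.2 asks for effort to obtain information on withdrawals. These make a Week 116 CDR-SB possible, but none of them requires one.

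The comparison is also between requests. Section 4.7.1 only asks people to return, and someone who has missed 14 to 16 weeks of dosing may decline. The group that matters is narrow: criterion met, study withdrawal chosen, event classed as SDCR, and a participant who would still have come. The plan also provides for residual missing data through CIR, a tipping-point analysis and the sample-size allowance. All of this stands. It limits the consequence without removing the difference in requested follow-up.

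**Conclusion.** The point holds as a modest, inexpensive improvement. For missed dosing alone the protocol permits a route whose requested visits leave the Week 116 window without a CDR-SB for 32 of 42 last-dose weeks on the printed dates, or 29 of 42 if the termination visit is held when the criterion is met.

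The counts assume nominal visit dates, an attended 50-week visit, and the consecutive-miss criteria only. The limb for half of the dosing visits in a calendar year is outside them.

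A reader might take 32 of 42 as a share of participants losing the primary endpoint, or as a measure of bias or lost power. The documents do not support that. These are schedule weeks; the number of participants withdrawn this way is not given, and no trial-level effect can be computed. Nor are study withdrawals left without any CDR, since the termination and 50-week visits both carry one.

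**What to change.** Reconcile section 4.7.2 with sections 3.1.1 and 4.7.1. State that missed dosing alone does not end study participation and that, unless consent is withdrawn, such participants are asked to attend the scheduled efficacy visits through Week 116, as 4.7.1 already provides for those off drug. Deleting the non-compliance bullet would not be enough, because the investigator's general right to withdraw a participant would remain. No dosing or treatment-stopping rule is proposed.

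The cost is a short amendment with ethics and regulatory approvals (Protocol 9.6). The visits are already in the schedule, but poorly compliant participants and their study partners would carry the burden of continuing them. The benefit is confined to Week 116 data not yet collected. SAP version 2 is dated 29 July 2022 and version 3 follows it, so few participants may still be in double-blind follow-up.

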4.7.3 Study Discontinuation

The Sponsor has the right to terminate this study at any time. Reasons for terminating the study may include, but are not limited to, the following:

- The incidence or severity of adverse events in this or other studies indicates a potential health hazard to participants.
- Participant enrollment is unsatisfactory.
- Futility analyses suggesting that treatment with gantenerumab is likely not effective.
- Sponsor determines it is the best interest of the participants.

The Sponsor will notify the investigator if the Sponsor decides to discontinue the study.

4.7.4 Site Discontinuation

The Sponsor has the right to close a site at any time. Reasons for closing a site may include, but are not limited to, the following:

- Excessively slow recruitment
- Poor protocol adherence
- Inaccurate or incomplete data recording
- Non-compliance with the International Council for Harmonisation (ICH) guideline for Good Clinical Practice
- No study activity (i.e., all participants have completed the study and all obligations have been fulfilled)

5. ASSESSMENT OF SAFETY

5.1 SAFETY PLAN

Gantenerumab is not yet approved, and clinical development is ongoing. The safety plan for participants in this study is based on clinical experience with gantenerumab in completed and ongoing studies. The identified risks for gantenerumab are outlined below. Please refer to the Gantenerumab Investigator's Brochure for a complete summary of safety information.

Several measures will be taken to ensure the safety of participants enrolled in this study. Eligibility criteria have been designed to exclude participants at higher risk for imaging-related abnormalities. Participants will undergo safety monitoring during the study, including assessment of the nature, frequency, and severity of adverse events. In addition, guidelines for managing adverse events, including criteria for dosage modification and treatment interruption or discontinuation, are provided below.

5.1.1 Risks Associated with Gantenerumab

5.1.1.1 Amyloid-Related Imaging Abnormalities

To date, clinical experience with gantenerumab reveals that ARIA events are dose-dependent and *APOE* ϵ 4 dependent. These events are manageable with MRI monitoring and dose intervention algorithms. In addition, in case of clinical symptoms, the use of IV glucocorticosteroids may be considered.

Rules for management of participants who develop ARIA-E or ARIA-H are provided in [Appendix 6](#).

5.1.1.2 Injection-Site Reactions

Gantenerumab may cause a reaction when given as an SC injection. In studies with gantenerumab, the most common events occurring more frequently with gantenerumab than with placebo were local ISRs, such as injection-site erythema. The majority of events were of mild intensity and resolved without treatment (see Section [1.2.3](#) for details).

Detailed information on the characteristic signs and symptoms of ISRs (e.g., erythema, pruritus) will be recorded on the dedicated eCRF page (see Section [5.3.5.2](#) for details on recording of ISRs).

5.1.1.3 Immunogenicity

As with administration of any exogenous protein, there is the potential for the development of ADAs, which can be neutralizing and/or sensitizing and which can potentially lead to febrile or allergic reactions, including anaphylaxis. The immunogenic risk of gantenerumab is considered low since it is a fully human antibody.

There are no clinical findings indicative of an immunogenic response to gantenerumab. Participants should be told how to recognize the signs and symptoms of hypersensitivity reactions and be monitored.

5.1.2 Management of Participants Who Experience Selected Adverse Events

Participants will undergo brain MRI examinations prior to every dose increase (pre-uptitration MRI scans) and according to the schedule of activities once the target dose is achieved. The pre-uptitration MRI scans will determine eligibility for the next uptitration dose. In the double-blind treatment period, a minimum of 3 doses of each dosing step have to be administered before the participant is eligible for the next uptitration dose. In the OLE, a minimum of 3 doses of each dosing step must be administered prior to be eligible for uptitration. In the OLE, a dose is defined as two consecutive dosing visits (one with an even dose number and one with an odd dose number, see [Table 4](#), Section [4.3.2.2](#)).

Participants will be eligible for uptitration if there are no new ARIA-E, if the ARIA-E is resolved (BGTS=0), and if the criteria for discontinuation because of ARIA-H have not been met.

In addition, the following dose adjustment and discontinuation rules for MRI findings will apply:

- In case of asymptomatic ARIA-E ≥ 1 and < 4 BGTS: Continue study drug at the same dose level (i.e., do not uptitrate) and repeat MRI 4 weeks later.

As long as BGTS is < 4 and ≥ 1 , continue study drug at the same dose level and continue MRI monitoring at 4-week intervals until the event resolves. When ARIA-E resolves, resume uptitration and MRI monitoring according to the schedule of activities.

If BGTS ≥ 4 or symptoms develop, refer to the rule below.

- In case of occurrence of symptoms in the presence of ARIA-E (any size) or asymptomatic ARIA-E with ≥ 4 BGTS: Temporarily interrupt study drug (but continue all assessments per schedule of activities) and implement MRI monitoring performed at 4-week intervals until symptoms and ARIA resolve.

When symptoms and ARIA-E resolve, reintroduce study drug at the next scheduled dosing visit, at the same dose given at the time the event was detected and perform an MRI scan after the first dose for participants on Q4W regimen and after the second dose for participants on the Q2W regimen.

If no new ARIA-E is detected, resume uptitration and obtain an MRI scan per the titration schedule. For participants on the Q2W regimen, perform another MRI scan 3 months after study drug reintroduction.

- In exceptional cases of 1) an ARIA-E that is asymptomatic with BGTS < 4 and that is considered stable over consecutive MRI images by the Sponsor and investigator; or 2) symptomatic ARIA-E for which the imaging evidence of ARIA-E has resolved but

the CNS symptoms continue, the study drug can either be reintroduced or uptitrated, as applicable, and 4-weekly MRI monitoring may no longer be necessary, as determined by the Sponsor and investigator.

- Symptomatic ARIA-E is defined as onset or worsening of CNS symptom(s) that is/are temporally associated with ARIA-E MRI findings.
- Any recurrence of ARIA-E: Treat using the same procedures as for the first event (based on symptoms and BGTS).
- Participants who develop > 15 ARIA-H cumulatively will be discontinued from study drug (the cumulative number should not include any disseminated leptomeningeal hemosiderosis, i.e., up to 3 focal leptomeningeal hemosiderosis *either on the same scan or cumulatively*; a focal leptomeningeal hemosiderosis is counted as an ARIA-H).
- In cases where both ARIA-E and ARIA-H occur, the most conservative approach should be followed.
- A PK sample and a plasma biomarker sample will be obtained as soon as is practical (e.g., at an unscheduled visit) once the site becomes aware of the occurrence or worsening of ARIA-E or ARIA-H that meet the discontinuation criteria.
- The investigators may choose to perform additional MRI monitoring for ARIA at any time.
- MRI monitoring of ARIA findings should be conducted at approximately 4-week intervals.
- Any other new significant findings will be reviewed by the medical monitor and appropriate dose action will be taken.

The iDMC reviews the incidence of ARIA in an unblinded manner and may recommend adjustment of dosing regimen and/or ARIA management for the overall study population or for a specific *APOE* ε4 genotype.

